5 STUDY ENDPOINTS

5.1 Evaluation of Efficacy

The primary effectiveness endpoint is the delivery of a standardized weekly Kt/V of greater than or equal to 2.1. The standardized weekly Kt/V value will be computed by the Sponsor and included in the study database from laboratory data provided/recorded by the site via the Case Report Forms (CRFs).

This analysis will be based on the Intent-to-Treat (ITT) population (section 11.1.1) with a supportive analysis for the Per-Protocol (PP) population (section 11.1.2).

5.2 Evaluation of Safety

The primary safety endpoint will be calculated using the mean number of adverse events from the prespecified list observed during a dialysis interval as follows:

- 1. Serious Adverse Event: any serious adverse event that:
 - Results in death,
 - Is life-threatening,
 - Requires hospitalization or prolongs existing hospitalization,
 - Requires intervention to prevent permanent impairment or damage, or
 - Results in persistent or significant disability/incapacity.
- 2. Allergic Reaction: Type A, anaphylactoid or Type B dialyzer reactions to dialyzer, blood tubing or chemical disinfectant.
- 3. **Blood Loss**: blood loss resulting in hemodynamic compromise that leads to death, transfusion or fluid resuscitation with greater than 1 liter of crystalloid IV fluids.
- 4. **Hemolytic Reaction**: hemolytic reactions due to disinfectant exposure, dialysate temperature, mechanical failure or other device related causes.
- 5. Infection: any infection related to catheter, its tunnel or exit site, AV fistula, or AV graft.
- 6. Intra-Dialysis Event: a significant clinical event such as loss of consciousness, cardiac arrest, or seizure caused by device failure.
- 7. Vascular Access Complication: defined as AVF or AVG clotting during the dialysis procedure, bleeding for more than 30 minutes post-dialysis for 3 consecutive sessions, difficulty with vascular access resulting in inability to initiate or complete dialysis treatments or complications related to hemodialysis catheters (not including reduced blood flow in catheter or TPA or catheter exchange).
- 8. **Pyrogenic Reaction**: onset of objective chills (visible rigors) and fever (oral temperature greater than or equal to 37.5 degrees Celsius) in a Subject who was afebrile and who had no recorded signs or symptoms of infection before treatment.

A dialysis interval is defined as the start of one dialysis treatment until the start of the next dialysis treatment. The primary safety analysis will be performed on the Intent-to-Treat (ITT) population.

5.3 Secondary Outcome Measure

The ultrafiltration (fluid removal) value as reported by the device will be within 10% of the expected fluid removal based on the UF prescription and the Tablo Console fluid removal algorithm.

5.4 Other Data and Analyses

Baseline and demographic characteristics will be summarized for all Subjects. Continuous variables will be displayed via summary statistics (mean, median, sample size, standard deviation, minimum, and maximum). Categorical variables will be summarized via counts and percentages. In addition, summary statistics will be computed on the number of pre-specified adverse events per dialysis interval for each treatment period. The same summary statistics will be calculated by treatment period for the rate of pre-specified adverse events per 100 dialysis treatments. Concomitant medications that may affect the study endpoints will also be collected and analyzed. These include, but are not limited to, blood thinners, diuretics, hypertensives and iron supplements.

6 STUDY DESIGN

6.1 Overview

This is a prospective, multicenter, open label, non-randomized, cross-over study. Subjects will be enrolled in the trial for approximately 21 weeks during which time Subjects will use the Tablo[™] Hemodialysis

System for dialysis treatments in all study phases. There are four periods during which the Tablo System will be utilized; run-in, treatment period 1, training/transition and treatment period 2.

• **Run-in** – Subjects will undergo dialysis treatment 4 times/week for 1 week In-Center. Treatments will be administered by study staff.

Confirmation of study eligibility will be assessed after the Subject completes this one-week run-in period.

• Treatment Period 1, In-Center – Subjects will undergo dialysis treatment 4 times/week for 32 treatments (approximately 8 weeks) In-Center. Treatments will be administered by study staff. Subjects are expected to undergo no more than 4 complete treatments per week during this treatment period.

Subjects are considered enrolled in the study if they meet all inclusion and exclusion criteria and have started the first study treatment during the first treatment period.

- In-Home Transition—Subjects will undergo device training for the study, then perform self-care dialysis 4 times/week for approximately 4 weeks. Treatments performed during the first portion will be completed In-Center under supervision. Treatments performed during the second portion will be completed In-Home. This second portion will assess subject stability in a new care environment. Supervision will be at the discretion of the Investigator.
- **Treatment Period 2, In-Home** Subjects will undergo self-care dialysis treatment 4 times/week for 32 treatments (approximately 8 weeks) In-Home. Subjects are expected to undergo no more than 4 complete treatments per week during this treatment period.
- **Follow-**Up---Subjects treatment modality will be followed for up to 5 years post study completion.

Figure 1: Study Design

Data collected during Treatment Period 1 and Treatment Period 2 will be used to assess the primary endpoints.

In the event a subject undergoes more than 4 complete treatments per week, during Treatment Period 1 and Treatment Period 2, the additional treatment(s) will be reported as a protocol deviation per Section 13.3.2.

6.2 Efforts to Minimize Bias

To maintain a balanced population in the study, no single Investigational Site will be permitted to enroll more than 30% of the entire study population.

6.3 Blinding and Randomization

This study is a prospective, multicenter, open label, non-randomized, cross-over study comparing In-Center and In-Home hemodialysis performance using the Tablo™ Hemodialysis System. Both Subjects and attending clinicians will know the System delivering dialysis treatments, therefore, blinding is not required.

Each Subject will serve as his or her own control in terms of treatment period comparisons (In-Center versus In-Home), and as such, randomization procedures are not required.

6.4 Clinical Events Committee

In order to minimize bias, an independent Clinical Events Committee (CEC) will assess clinical events to determine the following:

- Confirm whether or not the event should be included as one of the 8 pre-specified adverse events (defined in Section 9.1.5) that will be analyzed as the Primary Safety Endpoint for the study.
- Event was related to the device as defined in Section 9.2.3.
- Event was related to the dialysis procedure and is considered an additional treatment observation (ATO) as defined in Section 9.1.3. These adverse events are generally associated with dialysis and are a consistent with the Subject's established history on dialysis.
- Event was related to a pre-existing condition.

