9 ADVERSE EVENT REPORTING

9.1 Adverse Event Definitions

9.1.1 Adverse Event (AE):

An adverse event (AE) is any undesirable medical occurrence in a clinical study Subject, whether it is considered to be related to the device or not, that includes a clinical sign, symptom or condition.

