9.1.3 Additional Treatment Observations (ATOs)

Additional Treatment Observations (ATOs) are observations of interest that are not considered adverse events. These observations will be recorded as measured. These include, but are not limited to:

- Blood pressure measurements
- Phosphorous and potassium levels
- Alarms that end treatment
- Subjects feeling cold during treatment
- Study Subject drop out
- clinically significant alarms during treatment as reported by the Tablo Console
 - air in venous bloodline,
 - low systolic blood pressure,
 - high/low venous pressure, and
 - o blood leak in dialyzer

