9.2 Recording Adverse Events

9.2.1 Adverse Event Categorization

Reported Adverse Events will be categorized into one of the following two categories:

- 1. Primary Safety Endpoint: This category includes the 8 pre-specified adverse events that will be analyzed as the Primary Safety Endpoint for the study.
- 2. Other Adverse Events: This category includes all reported adverse events that meet the definition in Section 9.

The proposed categorization will serve to focus reporting, adjudicating, and analysis efforts to those categories most relevant for demonstrating the investigational device's relevant safety profile.

It is the intention of the Sponsor that AE's be collected in a uniform manner over the course of the study (independent of study arm) through the use of a Subject questionnaire. The Subject will be asked to complete a questionnaire regarding signs and symptoms experienced during each treatment. During regularly scheduled clinical follow-up visits during the trial, study staff will review the signs and symptoms noted by the Subject and provide education, as needed, on how they are documented. The study staff will determine whether subject reported signs and symptoms meet the definition of an AE as specified in Section 9. This approach attempts to eliminate any potential observed differences in AE rates between the study arms that are solely due to reporting sources or techniques.

Prior to analysis, all adverse events (AEs) will be coded using the Medical Dictionary for Regulatory Activities (MedDRA). Based on these coded terms, treatment emergent AEs will be summarized by treatment period, by severity, relation to procedure and relation to device.

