9.2.2 Other Adverse Events

The Investigator will monitor the occurrence of adverse events for each Subject during the course of the study. All AEs will be listed on the adverse event case report forms. All pre-existing medical conditions and baseline dialysis stability signs and symptoms will be recorded on baseline case report forms for medical history and signs and symptoms.

Starting with the first treatment during Treatment period 1 with the Tablo[™] Hemodialysis System, any new event/experience that was not present at baseline, or worsening of an event present at baseline, is considered an adverse event. Recorded Adverse Events will include, but are not limited to:

- infections (other than those defined in the Primary Safety Endpoint),
- hypotension,

Note: Unchanged, chronic conditions are not adverse events and should not be recorded on the adverse event page of the CRF.

Note: Laboratory values that are abnormal will not be considered as adverse events unless medical intervention is required. Clinical laboratory data will be monitored and values that are outside of the normal ranges will be separately summarized by time point for each treatment period (In-Center and In-Home). During the In-Center treatment period, summary statistics (mean, standard deviation, median, range, n) on laboratory values collected will be computed on the raw data. During the In-Home treatment period, summary statistics (mean, standard deviation, median, range, n) on laboratory values collected will be computed on the raw data. During the In-Home treatment period, summary statistics (mean, standard deviation, median, range, n) on laboratory values collected will be created for each laboratory values collected will be computed on the raw data. Individual tables will be created for each laboratory panel and quantitative parameter combination. In addition, a summary table will be created for each laboratory panel (hematology and chemistry) to display the number and percentage of subjects who have results that fall out of the normal ranges for each laboratory parameter by time point for each of Treatment Period 1 and 2.

Adverse events will be monitored until they are adequately resolved or explained. Should an adverse event be ongoing at the end of the Subject's last study treatment the medical care plan for the Subject will be described and documented.

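### Protocol 6.4 lets the CEC class a procedure-related adverse event as an ATO, which 9.1.3 says is not an adverse event, and nothing says such an event stays in the AE results

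*Protocol*

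**What the plan says.** Protocol 6.4 lists four matters for the CEC to determine. The first concerns the primary safety endpoint: "Confirm whether or not the event should be included as one of the 8 pre-specified adverse events". The third reads: "Event was related to the dialysis procedure and is considered an additional treatment observation (ATO) as defined in Section 9.1.3". The sentence after it describes the events so classed: "These adverse events are generally associated with dialysis and are a consistent with the Subject's established history on dialysis".

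Protocol 9.1.3 defines the class: "Additional Treatment Observations (ATOs) are observations of interest that are not considered adverse events". Its examples are readings, laboratory levels, alarms, feeling cold and drop-out, introduced by "These include, but are not limited to".

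Two other sections say what an adverse event is. Section 9.1.1 has "any undesirable medical occurrence in a clinical study Subject, whether it is considered to be related to the device or not". Section 9.2.2 says that, from the first treatment of Treatment Period 1, "any new event/experience that was not present at baseline, or worsening of an event present at baseline, is considered an adverse event".

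Section 9.2.1 says "Reported Adverse Events will be categorized into one of the following two categories". The two are the primary safety endpoint and Other Adverse Events. The same section plans AE summaries by relation to procedure as well as to device, and SAP Tables 18 and 20 have rows for the highest relationship of an AE to treatment.

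**The concern.** Sections 6.4 and 9.1.3 cannot both stand. An event that 6.4 calls an adverse event ceases to be one under 9.1.3 once the CEC gives it the ATO label. The two grounds in 6.4 for the label are relation to the dialysis procedure and consistency with the subject's dialysis history. Neither appears in the 9.1.3 definition, and the open list there sets no limit.

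The study evaluates a dialysis device and has no external control, so events tied to the dialysis procedure are a large part of what its safety results should show. Any loss through this route goes one way: it can lower the reported AE results but not raise them.

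**Working it through.** The check is mainly of the text, with one calculation for scale.

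1. **Can an event be an AE and be labelled ATO?** Yes. Section 6.4 itself uses the term adverse events for the ATO class. A new or worsened event is an AE under 9.2.2, and 6.4 does not exclude such events from the label. Section 9.1.1 expressly sets aside device relation only, but it makes no exception for relation to the procedure.

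2. **Where does a labelled event go?** Section 9.2.1 has two AE categories and ATO is neither. SAP 5.1 says that all AE tables are based on study-emergent AEs. An event that 9.1.3 says is not an AE therefore has no place in those tables.

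3. **Does the SAP settle it?** No. It mentions neither the CEC nor ATOs. It does not say whether the investigator's or the CEC's classification is analysed, or whether a relabelled event is kept. Outside the AE tables, SAP 4.2.3 reports alarms, feeling cold and hypotension, so those items would remain visible somewhere. Other procedure-related events would not.

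4. **Which events reach the CEC?** Under 9.2.4 it adjudicates AEs that the site calls device related, severe, or primary safety events, and it periodically reviews all AEs. Events outside the eight pre-specified types are thus within its reach.

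5. **Which results are exposed?**
   - Other Adverse Events: directly, through Tables 18, 19 and 21. No separate determination holds these events in the AE set.
   - Pre-specified events: less directly, through Tables 16, 17, 20 and 21. The first determination in 6.4 decides membership separately, but no rule says which determination prevails if an event meets a 9.1.5 definition and is also labelled ATO.

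6. **Scale for Table 16, if a pre-specified event were lost.** Protocol 11.8 plans 30 subjects with at least 32 treatments per period.
   - Intervals per period: 30 × 32 = 960.
   - Change in rate per event lost: 100 × 1/960 = 0.104 per 100 treatments.
   - Events needed to move the rate by the stated margin of 1 per 100: 0.01 × 960 = 9.6.

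The documents state no figure for relabelled events, so there is none to reproduce. They also give no expected count of events, so the total effect cannot be calculated.

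**The case against.** The best reply is that the plan does not treat relation to the procedure as grounds for removal. Section 9.2.1 and SAP Tables 18 and 20 report AEs by relation to procedure or treatment, which presupposes that such events stay in. This stands, and it shows what the analysis intends. It does not say what happens to an event that the CEC has labelled ATO; instead it adds another place with which 6.4 conflicts.

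A reader might infer that adjudication will take events out of the primary safety count. The documents do not support that. Endpoint membership is its own determination in 6.4, 9.2.4 has the CEC confirm it against the endpoint criteria, and none of the eight definitions in 9.1.5 excludes an event for being procedure related or consistent with dialysis history. No sentence orders deletion. What remains is the missing precedence rule.

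A reader might also set the 9.1.3 examples against 9.2.2, for instance low systolic pressure alarms against hypotension, and see a second contradiction. That is weak. A reading or an alarm can be an ATO while the clinical event behind it is an AE. Listing laboratory levels as ATOs is compatible with the 9.2.2 rule that an abnormal value is an AE only when medical intervention is required.

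Finally, 9.2.2 already excludes unchanged chronic conditions, so some events in keeping with a subject's history were never AEs. That narrows the problem to new or worsened events but does not remove it.

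**Conclusion.** The contradiction between 6.4 and 9.1.3 is real and should be resolved before adjudicated data are analysed. Followed literally, 6.4 lets the CEC move a new or worsened procedure-related event out of the AE set, against 9.1.1, 9.2.1 and 9.2.2 and against the planned summaries by relation to procedure. The direct exposure is the Other Adverse Events content of SAP Tables 18, 19 and 21.

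Loss from Table 16 is possible but not prescribed. Its scale is about 0.10 per 100 treatments for each event lost, assuming 960 intervals per period. Whether any pre-specified event would be lost, and how many, is unknown, so no estimate of bias in the primary safety rate is justified.

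**What to change.** - **Protocol 6.4:** make procedure-related/ATO an attribution flag. State that it does not remove a reported event meeting 9.1.1 or 9.2.2 from the AE set, and does not override a determination that an event meets a 9.1.5 definition.
- **SAP:** state that flagged events stay in the AE tables that apply to them (pre-specified events in Tables 16, 17, 20 and 21; all AEs in Tables 18, 19 and 21), and list the CEC attribution.
- **Protocol 9.1.3:** add only that recording an item as an ATO does not prevent an associated clinical event that meets 9.1.1 or 9.2.2 from being recorded as an AE. Leave the 9.2.2 laboratory rule as it is. Making every listed item an AE whenever it is new or worse than baseline would contradict that rule, because it would turn abnormal levels that need no intervention into AEs.

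The cost is wording in two protocol sections and the SAP, one flag variable and a listing. The downside is that reported AE counts may be slightly higher.

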7 SUBJECT SELECTION

7.1 Study Population

Subjects with a diagnosis of end stage renal disease (ESRD) who meet the inclusion and exclusion criteria will be eligible for participation in this study. The eligibility criteria for the TABLO study are designed to capture diverse Subjects, such as those patients who are currently undergoing In-Center, In-homehemodialysis, or peritoneal dialysis. In addition, Subjects with all vascular access types are eligible for the study and may include catheters, grafts, and fistulas. Potential study candidates should be screened for eligibility according to the study inclusion and exclusion criteria.

To be considered enrolled in the study, the Subject must meet all inclusion and exclusion criteria and have started the first study treatment during the first treatment period.

7.2 Informed Consent

IMPORTANT: The Code of Federal Regulations requires that the consent form signed by the Subject must be dated at the time consent is given. Also, medical records must contain documentation that informed consent was obtained prior to participation in a study. (21 CFR Parts 50 and 812)

The Investigator may determine whether potential Subjects are interested in participating in an investigation, but shall not request the written informed consent of any Subject to participate, and shall not allow any Subject to participate before obtaining Institutional Review Board (IRB) and FDA approval. The consent process shall begin before care is altered beyond the scope of a routine comprehensive examination for the purpose of participating in this study.

All Subjects in this research study should be completely informed about the purpose, duration, and pertinent details of the study. The informed consent process must be documented using a written form that has been approved by the IRB and includes all *Basic Elements of Informed Consent* and pertinent *Additional Elements* (21 CFR Part 50.25).

The Investigator must keep the original signed copies of all consent forms in the Subject's medical records and provide a copy to each Subject.

Appendix A outlines the screening and enrollment process and illustrates the point where informed consent should be obtained.

7.3 Subject Privacy

In accordance with the Health Insurance Portability and Accountability Act of 1996 (HIPAA), all Subjects should be informed of potential uses and disclosures of their medical information for research purposes, and their rights to access information about them by covered entities. Each Investigator will follow the procedures for securing HIPAA compliance as directed by their respective IRB or Privacy Board, and to obtain written authorization to use and disclose Subject information for all clinical research and research involving questioning of the Subject's or Subjects' physician(s). Per individual site procedures, this authorization may be included as part of the Subject informed consent form.

7.4 Inclusion Criteria

Subjects must meet **ALL** of the inclusion criteria to be enrolled in the study.

- 1. Subject has provided informed consent and has signed a Health Insurance Portability and Accountability Act of 1996 (HIPAA) compliant authorization statement.
- 2. Subject is at least 18 years and less than 75 years of age.
- Subject has end stage renal disease (ESRD) adequately treated by maintenance dialysis achieving a Kt/V ≥ 1.2 and has been deemed stable for at least three months by his/her treating nephrologist.
- 4. Subject has a well-functioning and stable vascular access that allows a blood flow of at least 300 ml/min.
- 5. Subject understands the nature of the procedures and the requirements of the study protocol, including home-based dialysis.
- 6. Subject is willing and able to comply with the protocol requirements and return to the treatment center for all required treatments and clinical evaluations.
- 7. Subject has identified an individual to be trained and available as needed. The identified individual must be considered competent in the use of the device by the prescribing physician.
- 8. Subject has a documented psychosocial evaluation by a qualified social worker, treating physician or home hemodialysis nurse.
- 9. Subject has no childbearing potential or has a negative pregnancy test within 7 days prior to the start of the first study treatment and will be utilizing medically acceptable means of contraception during the study period.

